6.20 Adverse Events

AE analyses will be presented by the actual treatment received for the Safety Population.

[REDACTED]

AEs will be collected from the time of informed consent through completion of the participant's last study visit.

A treatment-emergent adverse event (TEAE) is defined as:

- Any AE that has an onset on or after the first dose of study drug through completion of the last study visit.
- Any pre-existing AE that has worsened in severity on or after the first dose of study drug through completion of the last study visit.

AEs occurring prior to first dose of study drug are considered non-treatment emergent and will be listed only.

The Investigator will determine the relationship of the AE to treatment (related, not related). If an AE has missing relationship it is assumed to be related to the study drug for analysis purposes.

Severity of the AE will be graded using the Common Terminology Criteria for Adverse Events (CTCAE) grading system (Version 5.0): Grade 1 (mild), Grade 2 (moderate), Grade 3 (severe), Grade 4 (life-threatening), Grade 5 (fatal). Grade 3 (severe) will be assumed for an AE with missing grade.

An overall summary of AEs (number of participants with an event) will be presented by treatment group and overall, for the following:

- TEAE

[REDACTED]

[REDACTED]

Controlled Quality Management Document

Sponsor: Pliant Therapeutics Inc.

Protocol Number: PLN-74809-PSC-203

STATISTICAL ANALYSIS PLAN

Confidentiality Statement

This document [REDACTED] may not be duplicated, copied, altered or removed from company
without prior approval [REDACTED].

Controlled Quality Management Document

Sponsor:

Pliant Therapeutics Inc.

Protocol Number:

PLN-74809-PSC-203

STATISTICAL ANALYSIS PLAN

- TEAE related to study drug
- TEAE Related to a Study Procedure
- Serious TEAE
- Serious TEAE Related to Study Drug
- TEAE of CTCAE Grade 3 or Higher
- TEAE of CTCAE Grade 3 or Higher Related to Study Drug
- TEAE Leading to Interruption of Study Drug
- TEAE Leading to Withdrawal of Study Drug
- TEAE Leading to Early Termination from Study
- TEAE Leading to Death

Summaries of TEAEs (number of participants with an event) will be presented by system organ class and preferred term by treatment group for the following:

- TEAE
- TEAE Related to Study Drug
- Serious TEAE
- Serious TEAE Related to Study Drug
- TEAE Related to a Study Procedure
- TEAE of CTCAE Grade 3 or Higher
- TEAE of CTCAE Grade 3 or Higher Related to Study Drug

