- TEAE Leading to Withdrawal of Study Drug
- TEAE by SOC, PT and Maximum Grade (incidence only)
- [REDACTED]

The following listings of TEAEs will be presented in Section 14.3.2 of the CSR.

- TEAE Leading to Withdrawal of Study Drug
- TEAE Leading to Early Termination from Study
- TEAE Leading to Death
- Serious TEAE

System organ class will be presented in descending order of frequency in the pooled PLN-74809 group and then alphabetically. Preferred terms will be displayed in descending order of frequency in the pooled PLN-74809 group and then alphabetically.

Confidentiality StatementThis document [REDACTED]
without prior approval [REDACTED]

may not be duplicated, copied, altered or removed from company [REDACTED]

Controlled Quality Management Document

Sponsor:

[figure not shown]
Pliant Therapeutics Inc.

Protocol Number:

PLN-74809-PSC-203

STATISTICAL ANALYSIS PLAN

For summary by severity, participants reporting more than one AE per system organ class and preferred term will only be counted once for the most severe event.

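### The missing-grade rule makes no exception for a fatal outcome or a pre-dose severity, so it can misplace an ungraded death in the maximum-grade table and hide some worsening from the TEAE count

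*SAP*

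**What the plan says.** All of the following is in SAP Section 6.20 unless another section is named.

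- Severity is graded by CTCAE Version 5.0, and the upper end of the scale is given as "Grade 3 (severe), Grade 4 (life-threatening), Grade 5 (fatal").
- The next sentence is the missing-data rule: "Grade 3 (severe) will be assumed for an AE with missing grade". It speaks of an AE, not a TEAE, and sets no condition on onset or outcome.
- Collection starts before dosing: "AEs will be collected from the time of informed consent through completion of the participant's last study visit". Events arising in screening, which Section 1 allows to last up to 42 days, are therefore in the AE data and under the rule.
- A TEAE can qualify in two ways. The onset limb is "Any AE that has an onset on or after the first dose of study drug through completion of the last study visit". The worsening limb is "Any pre-existing AE that has worsened in severity on or after the first dose of study drug", over the same period.
- For the remainder, "AEs occurring prior to first dose of study drug are considered non-treatment emergent and will be listed only".
- The outputs include an overall summary with separate rows for TEAEs of Grade 3 or higher and for TEAEs leading to death, a listing of TEAEs leading to death, and a table by system organ class, preferred term and maximum grade.

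Section 3.1 makes TEAE incidence the primary safety endpoint. Section 6.8.3 counts AEs per participant. Section 5 plans 21 participants on each of four doses and 7 on placebo alongside each dose; Section 6.11 pools placebo across the study parts.

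The visible text does not say how worsening is established: by comparing grades, by an investigator flag, or by opening a new record.

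**The concern.** A default of Grade 3 reads as a worst-case rule, and for an event that starts after the first dose it mostly is one. In two situations it is not.

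For a death, the outcome already fixes the grade. Imputing Grade 3 replaces a value that can be deduced with one that the grading scale contradicts. Two safety displays in the same report could then disagree: one shows a death, the other shows no Grade 5 event.

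For a pre-dose severity, a high imputed grade raises the starting point. Worsening then becomes harder to show, so the rule can keep a true TEAE out of the primary endpoint. That is the opposite of what a worst-case rule is meant to do.

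**Working it through.** No figure in the SAP depends on this rule, so there is no stated number to reproduce. The check applies the rule as written.

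**1. Ungraded TEAE with fatal outcome**

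The rule gives Grade 3. Each display then behaves as follows, assuming that the death row and death listing come from the recorded outcome, as their titles suggest (the SAP does not give the derivation).

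| Display | Result |
|---|---|
| Maximum-grade table | Grade 3, unless the participant has a higher-graded event in the same class and term |
| Grade 3 or higher | counted, since 3 ≥ 3 |
| TEAE leading to death, row and listing | counted |
| Serious TEAE | counted if recorded as serious |

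Only the maximum-grade table is wrong.

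**2. Missing pre-dose grade**

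Suppose worsening is derived as post-dose grade > pre-dose grade. Take true pre-dose grades 1 to 4 and post-dose grades 1 to 5, which gives 4 × 5 = 20 pairs.

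- True worsening: 4 + 3 + 2 + 1 = 10 pairs.
- No worsening: 20 − 10 = 10 pairs.

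With the missing pre-dose grade set to 3, the test becomes post-dose grade > 3.

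- Worsening missed: 1 to 2, 1 to 3 and 2 to 3, so 3 of 10.
- Worsening kept: the other 7 pairs, all ending at Grade 4 or 5.
- False TEAE: only 4 to 4, so 1 of 10 non-worsening pairs.
- Both grades missing: 3 > 3 is false, so the event is not counted.

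With the missing pre-dose grade set to 1, the test becomes post-dose grade > 1.

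- Worsening missed: 0 of 10.
- False TEAEs: 2 to 2; 3 to 2 and 3 to 3; 4 to 2, 4 to 3 and 4 to 4. That is 1 + 2 + 3 = 6 of 10.

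These are counts of possible pairs, not probabilities; the pairs are not equally likely.

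**3. Missing post-dose grade of a pre-existing event**

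Here the current default helps. With a known pre-dose Grade 1 or 2, 3 > 1 and 3 > 2 both hold, and the event counts as a TEAE. With a known Grade 3 or 4 it does not. A corrected rule should therefore leave Grade 3 in place for post-dose severity.

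**4. Scale for the primary endpoint**

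Pooled placebo is 4 × 7 = 28. One participant lost from overall TEAE incidence is

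- 1/21 = 4.8 percentage points in a dose group;
- 1/28 = 3.6 percentage points in pooled placebo.

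Because counting is per participant, this happens only if that participant has no other TEAE.

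**The case against.** The strongest reply is that the second result depends on a derivation that the SAP does not state. If worsening is entered as a new record with onset on or after the first dose, the onset limb counts it whatever its grade. If the investigator flags it, the imputed grade does not decide whether it is a TEAE. Such recording rules are often left to the protocol or the case report form instructions, which are not at hand, and parts of Section 6.20 are redacted. This stands, and the second result is conditional on it. The first result is not: it holds however worsening is recorded.

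The conditions also stack up. Overall incidence moves only with a pre-dose event, a missing grade on it, true worsening that ends at Grade 3 or lower (or is also ungraded), a comparison of grades, no new record, and no other TEAE in that participant. This also stands, and it keeps the point minor.

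Three stronger readings are tempting, and the document does not support them:

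- *All worsening of an ungraded pre-dose event is lost.* Worsening to Grade 4 or 5 still counts.
- *The rule hides deaths.* An ungraded death is misplaced in one table and remains in the others.
- *Ungraded life-threatening events need their own Grade 4 rule.* The visible SAP describes no separate field from which that grade could be taken.

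Finally, a low default for every event with pre-dose onset would do harm. A pre-existing Grade 2 event whose post-dose grade is missing would then be set to Grade 1 and would no longer count as worsened. The distinction has to be when the severity applies, not when the event began.

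**Conclusion.** The point holds as a minor correction to a stated rule.

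- **Fatal outcome.** Followed literally, the rule contradicts the SAP's own definition of Grade 5 and can put the maximum-grade table out of step with the death row. It needs only one fatal TEAE left ungraded.
- **Pre-dose severity.** If worsening is found by comparing grades and no new record is opened, the rule is anti-conservative for the TEAE endpoint in 3 of the 10 worsening pairs and when both grades are missing.

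The expected effect is small. The SAP gives no frequency of missing grades; if there are none, nothing changes. Where every condition is met, each affected participant moves overall TEAE incidence by 4.8 points in a dose group or 3.6 points in pooled placebo, taking the planned group sizes.

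**What to change.** Replace the missing-grade sentence in Section 6.20 with:

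> A missing grade is set to Grade 5 if the AE outcome is fatal. Otherwise, a missing grade for severity on or after first dose is set to Grade 3, including the post-dose grade of a pre-existing AE. A missing pre-dose grade is set to Grade 1 only for judging whether a pre-existing AE worsened.

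Add a footnote to the affected AE tables giving the number of imputed grades.

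The cost is a short text change and a few lines of AE programming. The statistical price is over-counting: some ungraded pre-dose events that did not worsen will become TEAEs (6 of 10 non-worsening pairs against 1 of 10 now), and an event with both grades missing will count, since 3 > 1. That is the conservative direction for a safety endpoint, and the footnote shows how often it could have happened. One limit remains as now: a missing post-dose grade on an event with a known pre-dose Grade 3 or 4 and no fatal outcome will still not register as worsening.

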6.20.2 Laboratory Data

Descriptive statistics of the observed values and change from baseline will be presented by treatment group and visit for each continuous hematology, serum chemistry, coagulation, and urinalysis parameter. Shift tables for the change from baseline in categorical parameters will be presented in the natural order of the outcome where possible.

Summaries and listings will be presented using the Système International (SI) unit for each parameter as received from the analytical laboratory.

Each measurement (for continuous data where provided) will be classified as below, within, or above normal range based on ranges supplied by the laboratory used. Shift tables in relation to the normal range from baseline to each follow-up visit will be presented.

Clinical laboratory test parameters outside the reference ranges will be flagged. The incidence of treatment-emergent laboratory abnormalities (on or after first dose of study) will be summarized by severity and treatment group.

All individual laboratory data (including pregnancy testing data) will be listed.

Confidentiality StatementThis document [REDACTED]
without prior approval [REDACTED]

[REDACTED] may not be duplicated, copied, altered or removed from company [REDACTED]

Controlled Quality Management Document		
	Sponsor:	Pliant Therapeutics Inc.
	Protocol Number:	PLN-74809-PSC-203

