1 INTRODUCTION

This document details the planned statistical analyses for Pliant Therapeutics Inc. Study PLN-74809-PSC-203, “A randomized, double-blind, dose-ranging, placebo-controlled, Phase 2a evaluation of the safety, tolerability, and pharmacokinetics of PLN-74809 in participants with primary sclerosing cholangitis (PSC) and suspected liver fibrosis (INTEGRIS-PSC)”.

The proposed analyses are based on the contents of the [REDACTED]

[REDACTED]

This is a Phase 2a, multicenter, 3-part, randomized, double-blind, dose-ranging, placebo-controlled study to evaluate the safety, tolerability, and PK of once-daily (QD) treatment with PLN-74809 in male and female participants aged 18 to 75 years with an established diagnosis of large duct PSC and suspected liver fibrosis. Part 1 will evaluate 40 mg PLN-74809 and placebo, Part 2 will evaluate 80 and 160 mg PLN-74809 and placebo and Part 3 will evaluate 320 mg PLN-74809 and placebo. Placebo participants will be pooled across the study when comparing to PLN-74809 treatment groups.

Each study part will include an up to 42-day screening period, followed by a treatment period of either 12 weeks (Parts 1 and 2) or at least 24 weeks and up to 48 weeks (Part 3), and finally a 4-week post-treatment follow-up period. Based on regulatory considerations, randomization to dose level in Part 2 of the protocol (80 or 160 mg PLN-74809) was conducted in either parallel or sequential manner.

Each participant in Parts 1 and 2 will participate in the study for approximately 154 days (22 weeks), including screening, treatment, and post-treatment safety follow-up. The duration for Part 3 of the study will be variable depending on the study enrollment rate. The duration of participation will be approximately 238 days (34 weeks) for the last participant enrolled and approximately 406 days (58 weeks) for the first participant enrolled including screening, treatment, and post-treatment safety follow-up. The end of Part 3 will commence once the last participant reaches 24 weeks of treatment. At that time, all study participants will complete their next scheduled visit (End of Treatment [EOT]) and the 4 weeks of follow up (End of Study [EOS]). The end of study is defined as the last visit of the last participating participant.

Confidentiality Statement

This document [REDACTED] may not be duplicated, copied, altered or removed from company [REDACTED]
without prior approval [REDACTED]

	Controlled Quality Management Document	

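### Section 6.20.2 defines treatment-emergent laboratory abnormalities by timing alone, so an out-of-range value unchanged from baseline is counted and the any-grade and low-grade incidence is inflated in all arms

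*SAP*

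**What the plan says.** SAP Section 6.20.2 (Laboratory Data) first deals with range: "Clinical laboratory test parameters outside the reference ranges will be flagged". It then sets out the incidence table: "The incidence of treatment-emergent laboratory abnormalities (on or after first dose of study) will be summarized by severity and treatment group". The words in parentheses are the only definition offered.

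Section 6.20 (Adverse Events) uses the same term differently. A treatment-emergent adverse event needs either onset on or after first dose or, as the second limb, "Any pre-existing AE that has worsened in severity on or after the first dose of study drug through completion of the last study visit".

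Section 6.20.2 also plans displays that do refer to baseline. For continuous parameters, "Descriptive statistics of the observed values and change from baseline will be presented by treatment group and visit". For range categories (below, within, above), "Shift tables in relation to the normal range from baseline to each follow-up visit will be presented".

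The participants are adults "with an established diagnosis of large duct PSC and suspected liver fibrosis" (Section 1). Safety is the primary objective (Section 2.1), and clinical laboratories are a secondary safety endpoint (Section 3.2). Section 6.20 names CTCAE version 5.0 for grading adverse events. Section 6.20.2 names no severity scale for laboratory results.

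**The concern.** A treatment-emergent count is meant to show what appeared or got worse after dosing. Under Section 6.20.2 a liver test that was raised before the first dose and stays at the same level meets the definition at its unchanged severity. In a chronic liver disease this could apply to many participants on placebo and on each dose. The table would then mix pre-existing disease with on-treatment change, and its label would not tell the reader so.

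The other categorical display does not fill the gap. The shift tables have three levels, so a value already above range that rises further is still recorded as above at both times. No display in the visible text counts the participants whose laboratory severity rose from baseline. The definition also feeds more than one readout, because Section 7 applies all planned final analyses at both interim analyses.

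**Working it through.** **Inputs from the SAP.** Section 5 gives 21 active and 7 placebo participants for each of four doses: 4 × (21 + 7) = 112, which reproduces the stated total. That is 4 × 21 = 84 active and, with placebo pooled under Section 6.11, 4 × 7 = 28 placebo. The SAP states no laboratory event rate, no baseline abnormality rate, and no planned test on this table.

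**Assumptions.**
- b is the share of participants whose value for a given test is abnormal at baseline and stays abnormal.
- p is the probability of a new or worsened abnormality, taken as 10% on placebo and 30% on a dose.
- p is independent of baseline status, and b is the same in both arms.

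**Step 1: any-grade incidence under the two definitions.**
- Referenced to baseline: p.
- Timing only: b + (1 − b)p. Everyone in the share b is counted, whether or not they worsen.
- Difference between arms under timing only: (1 − b)(0.30 − 0.10) = (1 − b) × 20 points.

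| b | Dose, timing only | Placebo, timing only | Difference |
|---|---|---|---|
| 0 | 30% | 10% | 20 points |
| 0.5 | 0.5 + 0.5 × 0.30 = 65% | 0.5 + 0.5 × 0.10 = 55% | 10 points |
| 0.8 | 0.8 + 0.2 × 0.30 = 86% | 0.8 + 0.2 × 0.10 = 82% | 4 points |

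With the baseline-referenced definition the result is 30% versus 10% in every row.

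**Step 2: higher severities.** The table is split by severity. For reaching a given high severity, the relevant share is those already at that severity at baseline, which is normally smaller than b. With the same 30% and 10% applied to that severity:
- 5% already there: 0.05 + 0.95 × 0.30 = 33.5% versus 0.05 + 0.95 × 0.10 = 14.5%, a difference of 19 points.
- 10% already there: 0.10 + 0.90 × 0.30 = 37% versus 0.10 + 0.90 × 0.10 = 19%, a difference of 18 points.

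The dilution therefore falls on any-grade and low-grade counts and is slight where the severity is rare at baseline.

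**Step 3: what the other displays can show.**
- Change-from-baseline statistics include minimum and maximum (Section 6.8.3). One large rise at a scheduled visit would be visible, but the number of participants who worsened would not.
- Normal-range shift tables show movement into the abnormal range, but not further movement within it.
- The MMRM for ALP (Section 6.18.2) compares each dose with placebo by visit, for ALP.

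**The case against.** The strongest reply is that the laboratory analysis as a whole is not blind to baseline. Change from baseline is summarized for every continuous parameter, shift tables start from baseline, ALP has its own model, and all individual values are listed. A move from mild to severe would still appear in a higher row of the severity table. All of this stands, and it limits the point to one descriptive table.

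A reader might infer that the rule would hide a drug signal, or that liver-test incidence would sit near its ceiling in every arm. The SAP supports neither. It gives no frequency of abnormal tests at baseline, the limits on entry belong to a protocol not shown, and Step 2 shows little loss at severities that are rare at baseline. Parameters mostly normal at baseline are hardly touched.

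It can also be said that the parenthesis only gives an observation window, with worsening implied by the term itself or by the definition in Section 6.20. That reading is possible. But the authors wrote out the worsening limb for adverse events and left it out here, so two programmers could build two different tables. Some neighbouring text is redacted and Section 6.20.1 is not visible. The sentence itself is complete and carries its own condition. Finally, a severity scale that grades relative to baseline would soften the problem, but none is named.

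**Conclusion.** The point holds for the treatment-emergent laboratory incidence table. Read literally, Section 6.20.2 counts stable pre-existing abnormalities as treatment-emergent, which does not agree with how Section 6.20 uses the term. For any-grade counts a true difference is multiplied by (1 − b). Under the assumed rates, 20 points become 10 at b = 0.5 and 4 at b = 0.8, and stay at 20 when b = 0. Both b and the rates are assumptions. That liver tests are the ones affected is a reasonable expectation in PSC, not a figure in the SAP.

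The consequence is a mislabelled and diluted table, together with the lack of any count of participants whose severity worsened. It is not a failure of the whole laboratory safety analysis. It should be corrected because safety is the primary objective and the correction is small.

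**What to change.** In Section 6.20.2:

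1. Define a treatment-emergent laboratory abnormality as one observed after first dose with a severity grade higher than the participant's baseline grade. Use the baseline of Section 6.2.3 and count normal as grade 0.
2. Name the laboratory severity scale, and say how it grades a participant whose baseline is already abnormal.
3. Tabulate incidence by worst post-baseline grade on that basis. State whether unscheduled values count towards the worst grade, since Section 6.7 keeps them out of summaries.
4. Add a shift table of baseline grade against worst post-baseline grade for the liver parameters.

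**Cost.** A few sentences and modest programming, with no new data. Reported counts will fall, and a stable high-grade baseline value will appear only in the grade shift table and the listings, not in the incidence table. Under Section 6, a change made after unblinding for the Part 1/2 interim analysis has to go into an addendum, so it is best settled before then.

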6.20.3 Vital Signs

Descriptive statistics for observed values and changes from baseline in the following vital signs will be presented by treatment group at each visit:

- Systolic blood pressure (mmHg)
- Diastolic blood pressure (mmHg)
- Pulse rate (bpm)
- Body temperature (degrees Celsius)

All vital sign data will be listed.

For more information, contact the Office of the Vice President for Research and Economic Development at [contact] or [contact].

111

For more information, contact the Office of the Vice President for Research and Economic Development at [contact] or [contact].

11. **What is the primary purpose of the *Journal of Clinical Endocrinology and Metabolism*?**

10. **What is the primary purpose of the study?** (check all that apply)

a. To evaluate the effectiveness of a new treatment for a specific condition.

b. To determine the safety and side effects of a new drug.

c. To compare different treatment regimens for a particular disease.

d. To study the natural history of a disease or condition.

e. To explore the underlying mechanisms of a disease.

f. To develop a new diagnostic test or screening method.

g. To evaluate the cost-effectiveness of different medical interventions.

h. To assess the quality of care provided in different healthcare settings.

i. To evaluate the impact of environmental factors on health outcomes.

j. To study the genetic factors associated with a disease.

k. To evaluate the impact of lifestyle factors on health outcomes.

l. To develop new guidelines for the management of a disease.

m. To evaluate the impact of healthcare policies on patient outcomes.

n. To study the impact of social determinants of health on health outcomes.

o. To evaluate the impact of healthcare delivery models on patient outcomes.

p. To study the impact of healthcare access on health outcomes.

q. To evaluate the impact of healthcare costs on patient outcomes.

r. To study the impact of healthcare quality on patient outcomes.

s. To evaluate the impact of healthcare policies on healthcare delivery models.

t. To study the impact of healthcare delivery models on healthcare costs.

u. To evaluate the impact of healthcare quality on healthcare access.

v. To study the impact of healthcare access on healthcare quality.

w. To evaluate the impact of healthcare policies on healthcare delivery models.

x. To study the impact of healthcare delivery models on healthcare quality.

y. To evaluate the impact of healthcare access on healthcare delivery models.

z. To study the impact of healthcare quality on healthcare access.

Digitized by [contact]

Digitized by [contact]

Confidentiality Statement
This document [REDACTED] may not be duplicated, copied, altered or removed from company [REDACTED]
without prior approval [REDACTED]

Controlled Quality Management Document

Sponsor: Pliant Therapeutics Inc.

Protocol Number: PLN-74809-PSC-203

STATISTICAL ANALYSIS PLAN

